- o For both studies the post-treatment period starts on the day after the treatment period and ends on the day of the patient's last contact date within the study.

• For safety endpoints except for ERG:

- The on-treatment period for the parent study spans the time during which the study treatment is administered from the CS2 Study Day 1 until 7 days after the last dose of medication in the parent study. The on-treatment period for the OLE study is from the CS3 Study Day 1 until 7 days after the last dose of medication in the OLE study.
- For both studies the safety post-treatment period starts on the day after the safety treatment period and ends on the day of the patient's last contact date within the study.
- For both studies the Safety on-study period spans the time drug is first administered until the day of the patient's last contact date within the study.
- The period for the longitudinal safety analysis spans the time from the first dose of ISIS
 420915 in the parent study and ends on the day of the patient's last contact date within the study. The subject's last contact date is defined as follows:
 - (1) for subjects who signed an informed consent form in the OLE study, it is the last contact date within the OLE study;
 - (2) for subjects who did not sign an informed consent form in the OLE study but had been administered ISIS 420915 in the parent study, it is the last contact date within the parent study. The details of longitudinal safety analysis for AEs and safety lab results will be addressed in section 3.3.

For ERG:

The on-treatment period for the parent study spans the time during which the study treatment is administered from the CS2 Study Day 1 until 28 days after the last dose of medication in the parent study. The on-treatment period for the OLE study is from the CS3 Study Day 1 until 28 days after the last dose of medication in the OLE study.

- For both studies the safety post-treatment period starts on the day after the safety treatment period and ends on the day of the patient's last contact date within the study.
- The PK on-study period for the OLE study spans the time ISIS420915 is administered in the OLE study (CS3 Study Day 1) until the day of the patient's last contact date within the OLE study.

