3.2.1.4 Data Summary Plan

The table below details what data will be included in the summary and analysis output by endpoint type. Data summarized or analyzed at each interim analysis will be based on data collected up to the data cut date. It is possible that on-treatment data and post-treatment data available for each interim analysis is different from the final analysis at the end of study because data collected after each interim analysis data cut may slot into different treatment period. Outputs will be updated for each interim analysis and for the final analysis. In select instances the data for a type of endpoint that is summarized or analyzed may not be consistent with the rules in the table below; such exceptions will be noted in this document.

Endpoint type	Output type	Comment/definition
Efficacy	-Listings -On-treatment (CS2&CS3) summary/analysis tables -Post-treatment summary tables	-On-treatment (CS2 period):The CS2 Study Day 1 S Date of assessment S Last dose date in parent study+ 52 days -On-treatment (CS3 period): CS3 STUDY DAY 1 \$ Date of assessment S Last dose date of OLE study+ 52 days -showing both CS2 visits and CS3 visits. Note the results of the analyses at the CS2 visits will not be the same as the results from the CS2 study as this table only includes patients in the CS3 FASPost-treatment: Date of assessment > last dose date of OLE study + 52 days -Visit defined by analysis visit window
PD, BMIand mBMI	-Listings -On-treatment (CS2&CS3) summary/analysis tables -Post-treatment summary tables	-On-treatment (CS2 period): The CS2 Study Day 1 S Date of assessment S Last dose date in parent study+ 28days -On-treatment (CS3 period): CS3 STUDY DAY 1 S Date of assessment S Last dose date of OLE study+ 28days -showing both CS2 visits and CS3 visits. Note the results of the analyses at the CS2 visits will not be the same as the results from the CS2 study as this table only includes patients in the CS3 FAS.

Endpoint type	Output type	Comment/definition
		-Post-treatment: Date of assessment> last dose date+ 28days -Visit defined by analysis visit window
Safety Endpoints: ECG, Lab, vitals sign (including body weight)	-Listings -On-treatment summary tables (CS3) -Post-treatment summary tables	-On-treatment (CS3 period): CS3 Study Day Is Date of assessment 5 Last dose date + 7 days -Post-treatment: Date of assessment> last dose date+ 7 days -Visit defined by analysis visit window

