Safety Endpoints: ERG and ophthalmology examinations	-Listings -On-treatment summary tables (CS3) -Post-treatment summary tables	-On-treatment (CS3 period): CS3 Study Day ls Date of assessment 5 Last dose date+ 28 days -Post-treatment: Date of assessment> last dose date+ 28 days -Visit defined by analysis visit window
Safety Endpoints: abnormal lab, worst ECG, meeting Stopping rule	-Listings -On-study summary tables (CS3)	-Abnormal lab analyses described in Sections 3.3.4.1 to 3.3.4.3 include post-baseline data collected from CS3 Study Day 1 up to the day of the patient's last contact date within the study
Safety Endpoints: AE	-Listings -On-treatment (CS3) summary tables -On-study (CS3) summary tables	-On-treatment: CS3 Study Day ls Date of assessment 5 Last dose date + 7 days -On-study summary tables includes all treatment emergent adverse event (TEAE) in the OLE study, including those with onset dates> last dose date + 7 days
Selected Safety Endpoints: abnormal lab and AEs	- Longitudinal safety summary for overall parent study and OLEstudy	- Longitudinal safety summary for overall parent study and OLE study include data collected from the first dose of ISIS 420915 in the parent study and ends on the day of the patient's last contact date within the study, (1) for subjects who enrolled in the OLE study, it is the last contact date within the OLE study; (2) for subjects who are not enrolled in the OLE study but had been administered ISIS 420915 in the parent study, it is the last contact date within the parent study.
Concomitant medications	-Listings -On-treatment (CS3) summary tables -On-study (CS3) summary table	-On-treatment: CS3 Study Day ls Date of assessment s Last dose date + 7 days -On-study summary tables includes all concomitant medication in the OLE study, including those with onset dates > last dose date+ 7 days
Immunogenicity	-Listings -On-study (CS2 and CS3)	-On-study summary/analysis tables include data collected from the CS2 Study Day 1 up to the day of the

Endpoint type	Output type	Comment/definition
	summary/ analysis tables	patient's last contact date within the study (showing both CS2 visits and CS3 visits) -Visit defined by analysis visit window.
PK	-Listings -On-study (CS3) summary/ analysis tables	-Summary/analysis tablesinclude data collected from CS3 Study Day 1 up to the day of the patient's last contact date within the study -PK concentration will be summarized based onnominal scheduled visits (showing CS3 visits)

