3.3.2.7 Longitudinal Safety Analysis of TEAEs

For this summary TEAEs are defined as those events which first occurred or worsened on or after first dose of ISIS in the parent study.

Adverse events summaries including data from the combined study periods of the parent and OLE studies will be provided for subjects in the LSS analysis population. These summaries will include all TEAEs which started on or after the first dose of ISIS 420915 in the parent study and before the day of the patient's last contact date. For subjects who enrolled in the OLE study, the last contact date would be the one obtained from the OLE study. For subjects who are not enrolled in the OLE study the last contact date would be the one obtained from the parent study. Note that AEs which started during the gap period between the completion of the parent study and the first dose of the OLE study and are not considered TEAEs in the OLE study will still be included in these summaries. In other words, it is possible that there will be events which are not considered parent study TEAEs or OLE study TEAEs, but will be counted towards this analysis.

These TEAEs will be summarized for subgroups defined by the following variables: Age at parent study screening (<65 years and >=65 years), Sex (Female and Male), Race, Region (North America, Europe and South America /Australasia), and CM-ECHO Set (Included and Not Included). Results will not be provided for a variable if the overwhelming majority of patients are within one level of the subgroup.

Summaries of drug related TEAEs, TEAEs by maximum severity, adverse events leading to early withdrawal from Study Drug, TEAEs duration of exposure to Study Drug at the start of event (< 6 months, \geq 6 months to < 12 months, \geq 12 months to < 24 months, \geq 24 months to < 36 months, \geq 36 months to < 48 months, \geq 48 months to < 60 months, and \geq 60 months)and Number of doses at the start of event (26, \geq 26 to < 52, \geq 52 to < 65, \geq 65 to < 104, \geq 104 to < 156, \geq 156 to < 208, \geq 208 to < 260, \geq 260) will also be provided. Duration of exposure and the number of doses is calculated from **Day 1 of ISIS 420915** to the start date of event.

TEAEs in the following categories will also be summarized in tables and listed separately:

- Adverse events of special interest (defined in section 3.3.2.1)
- Other adverse events of interest (defined in section 3.3.2.2)

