3.3.4.1 Hepatobiliary Laboratory Abnormalities

The number and percentage of patients falling in each of the following categories based on all post-baseline assessments of the OLE study, including scheduled and unscheduled assessment on-study

period which spans the time drug is administered until the day of the patient's last contact date within the study, will be provided:

- ALT ≥ 3x Upper limit of normal (ULN) and total bilirubin ≥ 2xULN (with both events for any postbaseline results)
- Confirmed ALT ≥ 3x Upper limit of normal (ULN) and confirmed total bilirubin ≥ 2xULN (with both events for any post-baseline results)
- ALT ≥ 3xULN and international normalized ratio > 1.5 (with both events for post-baseline results)
- ALT ≥ 3xULN and total bilirubin ≥ 2xULN and ALP < 2xULN (with all three events for any postbaseline results)
- Hepatocellular injury
- Hepatocellular injury and total bilirubin ≥ 2xULN (with both events for any post-baseline results)
- ALT ≥ 3xULN
- ALT ≥ 5xULN
- ALT ≥ 8xULN
- ALT ≥ 10xULN
- ALT ≥ 20xULN
- Confirmed ALT ≥ 3xULN
- Confirmed ALT ≥ 5xULN
- Confirmed ALT ≥ 8xULN
- Confirmed ALT ≥ 10xULN
- Confirmed ALT ≥ 20xULN
- ALT ≥ 3xULN < 5xULN
- ALT ≥ 5xULN < 10xULN
- ALT ≥ 10xULN < 20xULN
- Total bilirubin ≥ 2xULN
- ALP ≥ 2xULN and (ISIS 420915 baseline ALP < 2xULN or ISIS 420915 baseline ALP missing)
- ALT \geq 3x ULN and ALT \geq 2 x ISIS 420915 baseline
- Confirmed ALT ≥ 3x ULN and confirmed ALT ≥ 2 x ISIS 420915 baseline

For patients that had ALT elevation ≥ 3 xULN, the time from CS3 Study Day 1 to first ALT elevation ≥ 3 xULN will be summarized using the following descriptive statistics: mean, standard deviation, median, P25, P75, and minimum and maximum.

Shift tables from baseline for ALT, AST, and total bilirubin based on peak (maximum) and confirmed peak category will also be provided. Categories for the ALT and AST shift tables will be $< 3 \times ULN$, $\ge 3 \times ULN$, $\ge 5 \times ULN$, and $\ge 8 \times ULN$. Categories for the total bilirubin shift table will be $< 2 \times ULN$ and $\ge 2 \times ULN$.

A hepatocellular injury event is defined as $(ALT/ALT\ ULN)/(ALP/ALP\ ULN) \ge 5$ and $ALT \ge 3xULN$, with the ALT and ALP assessments done on the same day.

The categories listed above will also be analyzed using AST instead of ALT. For these analyses the definition of hepatocellular injury will not be changed to depend on AST.

3.3.4.2 *Platelets*

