3.3.4.4 Longitudinal Safety Analysis of Laboratory Measurements

Laboratory measurements summaries including data from the combined study periods of the parent and OLE studies will be provided for subjects in the LSS analysis population. These summaries will include lab results specified in this section which occurred on or after the first dose of ISIS420915 in the parent study and before the day of the patient's last contact date For subjects who enrolled in the OLE study, the last contact date would be the one obtained from the OLE study. For subjects who are not enrolled in the OLE study, the last contact date would be the one obtained from the parent study:

- Hepatobiliary laboratory abnormalities (defined in section 3.3.4.1);
- Platelets (defined in section 3.3.4.2);

Note: For longitudinal safety analysis, Time to events will be started from **Day 1 of ISIS 420915** instead of **Study Day 1**.

• Renal parameters (defined in section 3.3.4.3)

Summaries for these abnormal lab test results will be provided for patients on active treatment in the parent study in LSS.

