9.2.2.2 Study Period Definition (On-Treatment, Post-Treatment and On-Study)

On-Treatment

- For efficacy endpoints except BMI, mBMI and PD, on-treatment period starts from ISIS
 420915 Study Day 1 until 52 days after the last dose of ISIS 420915.
- For BMI, mBMI, PD and Safety endpoint ERG, on-treatment period is from ISIS 420915 Study
 Day 1 until 28 days after the last dose of ISIS 420915
- For other Safety endpoints except ERG, on-treatment period is from ISIS 420915 Study Day
 until 7 days after the last dose of ISIS 420915

Post-Treatment

Post-treatment period starts on the day after the on-treatment period and ends on the day
of the patient's last contact date within the study.

On-Study

On-Study starts from ISIS 420915 Study Day 1 until the patient's last contact date.

Of note, the definition above only apply for CS2 and CS3 combined data summary, which is not conflict with section 3.2.1.1.4

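### The SAP gives two end dates for the longitudinal safety analysis; the analysis sections, read literally, leave out adverse events and labs dated on the last contact day

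*Combined protocol and SAP*

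**What the plan says.** Four places in the SAP set the upper date limit of the longitudinal safety analysis.

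- 3.3.2.7, adverse events: events from first dose "in the parent study and before the day of the patient's last contact date".
- 3.3.4.4, liver, platelet and renal labs: results "which occurred on or after the first dose of ISIS420915 in the parent study and before the day of the patient's last contact date".
- 3.2.1.1.4, the formal period definition: the period starts at first dose "in the parent study and ends on the day of the patient's last contact date within the study".
- 3.2.1.4, the Data Summary Plan row for longitudinal abnormal labs and adverse events: "data collected from the first dose of ISIS 420915 in the parent study and ends on the day of the patient's last contact date".

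Section 3.2.1.4 allows departures from its table, saying that data for some endpoints "may not be consistent with the rules in the table below; such exceptions will be noted in this document". Neither 3.3.2.7 nor 3.3.4.4 is marked as such an exception.

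The SAP states which study supplies the last contact date (the extension for patients who entered it, otherwise the parent study). It does not say how the date is set.

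**The concern.** The day at issue is not an arbitrary one. In the extension, chemistry, hematology and urinalysis are scheduled at both the early termination visit and the post-treatment visit (protocol Appendix A). Recording of non-serious adverse events stops at the final post-treatment visit (protocol 9.4.2), and a patient who withdraws consent leaves observation on the date of the request (protocol 8.9). A final visit or a death is therefore a plausible last contact date, and a rule that cuts off that day would remove records that matter for safety.

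Safety and tolerability are the primary objective (SAP 1.2.1). The LSS tables are the only adverse event and liver, platelet and renal lab tables specified in this SAP itself that run from first dose in the parent study. Section 9.2.2 brings in other combined outputs but refers to a separate SAP for their definition, and section 9.1 does not remove the longitudinal analysis.

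**Working it through.** No sample size or power figure is involved. The check compares two date rules and then asks which records differ. Write L for the last contact date.

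**Which rule stands where**

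| SAP section | Upper limit | Record dated L |
|---|---|---|
| 3.3.2.7 (adverse events) | date < L | excluded |
| 3.3.4.4 (labs) | date < L | excluded |
| 3.2.1.1.4 (period definition) | date ≤ L | included |
| 3.2.1.4 (summary plan row) | date ≤ L | included |

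Two further places lean towards inclusion. Section 9.2.2.2, for combined parent and extension summaries, says "On-Study starts from ISIS 420915 Study Day 1 until the patient's last contact date" and declares itself not in conflict with 3.2.1.1.4. The hepatobiliary categories that 3.3.4.4 reuses come from a section whose period "spans the time drug is administered until the day of the patient's last contact date". The word used there is less decisive than in 3.2.1.1.4, but neither place removes the last day.

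The two rules differ by one calendar day per LSS patient.

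**Which records change**

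1. Fatal event with onset on the day of death. If L is the date of death, the strict rule removes it from the longitudinal tables by preferred term, severity, relatedness and event of interest. The death itself stays in, because 3.3.2.5 counts deaths after first dose with no last-contact limit and 3.3.2.7 applies that summary to the LSS.
2. Lab drawn at the final visit on date V. If L = V, the strict rule removes it. If any later contact is recorded, L > V and the lab is kept under both rules.
3. Adverse event reported at the final visit with an earlier onset. It is kept under both rules, because the limit applies to the start date.
4. Normal retest on day L, within 7 days of an abnormal value. The strict rule removes the retest. Under 3.3.4 an abnormal value with no retest within 7 days is presumed confirmed, so the confirmed count can rise.

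**Where else the record would appear**

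- LSS patient dosed in the extension: last-day extension events and abnormal labs stay in the CS3 on-study tables (3.2.1.4, 3.3.2.6, 3.3.4.1 to 3.3.4.3).
- LSS patient who never entered the extension: 3.2.2 includes these patients in the LSS, and no other adverse event or liver, platelet or renal lab table specified in this SAP holds their records.

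**Size**

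SAP 1.1 plans 135 patients randomized 2:1, so the active arm is 135 × 2/3 = 90. One patient is 1/90 = 0.011, or 1.1 percentage points. The tables count patients, so a row moves by this amount only when the lost record is the patient's sole qualifying one for that row. For k such patients in one row the change is k × 1.1 points: 1.1 for one, 2.2 for two, 3.3 for three. The documents do not allow k to be estimated.

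**The case against.** The strongest reply is that the inclusive rule is plainly intended. The formal definition and the summary plan row written for this very analysis both include the last day, departures were to be noted and none is, and 9.2.2.2 agrees. On this view the two analysis paragraphs are merely loosely worded. That is probably right about intent, and it defeats the inference that the SAP has settled on excluding the last day. It does not remove the contradiction, because the strict wording appears twice, in the sections that specify the tables.

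A second reply is that the effect depends on a date the SAP never defines. This stands. Nothing in the documents says that last contact equals the date of death or the final visit, and protocol 9.4.1 foresees SAE follow-up past the last scheduled visit. For patients who did not enter the extension, the visit schedule is that of the parent protocol, which is not among these documents. A reader might infer that every final-visit lab is lost; that does not follow.

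A third reply is redundancy. Platelets are monitored weekly and creatinine every 2 to 3 weeks on treatment and for at least 6 weeks after the last dose (protocol 8.5.4, 6.1.3 and Appendix C), so a single last-day value will often duplicate an earlier one. Protocol 10.6.2 also calls for narratives of deaths and serious events, and all extension data are listed (SAP 3.2.1). This limits the size of the problem. It does not restore the missing entries in the longitudinal tables, and for patients outside the extension the CS3 tables and listings offer no cover.

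**Conclusion.** The point holds as an internal contradiction with a limited, conditional effect. If 3.3.2.7 and 3.3.4.4 are programmed literally, adverse events starting and labs drawn on the last contact date are missing from the LSS tables. The exposure is greatest for active parent-study patients who did not enter the extension. The size is about 1.1 points per row for each patient whose sole qualifying record is lost. This assumes the planned 90 active patients as denominator and a last contact date equal to the event or draw date.

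Three stronger conclusions might be drawn, and the documents support none of them. Deaths do not vanish from the report, because the LSS mortality summary has no such cut. Risk is not always understated: dropping records can only lower adverse event and unconfirmed lab counts, but dropping a normal last-day retest can raise a confirmed count. Nor does each lost event shift a percentage, since the tables count patients rather than events.

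This is a small correction, worth making because safety is the primary objective and the change is nearly free.

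**What to change.** In SAP 3.3.2.7 and 3.3.4.4, change the upper limit to on or before the day of last contact, so that both match 3.2.1.1.4 and 3.2.1.4. In 3.2.1.1.4, state how the last contact date is set: which recorded dates feed it (visits, phone contacts, later safety follow-up) and what applies when a patient dies. The definition is needed as well as the inclusive wording. If last contact were set at a date before death, a fatal event with onset on the day of death would still fall outside the period.

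The cost is two added words in each of two paragraphs, one short definition, and one comparison operator in the adverse event and lab programs. No new data collection is needed.

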3.3.3 Vital Signs, Weight, and Physical Examination Findings

Vital signs include systolic and diastolic blood pressure, pulse, respiratory rate, and temperature. Weight will also be analyzed. Absolute value at each visit, change and percent change from ISIS 420915 baselines to each visit in vital signs and weight will be summarized by treatment group of the parent study. Same summary for weight will also be presented based on the parent study baseline and the OLE study baseline. No statistical comparisons between treatments will be performed for this summary.

All vital signs and weight will be listed. Physical examination findings will also be listed.

3.3.4 Laboratory Measurements

Laboratory tests to ensure patient safety include chemistry panel, complete blood count with differential, thyroid panel, coagulation panel, immunogenicity, inflammatory panel, complement, and urinalysis. Absolute value, change and percent change from **ISIS 420915 baselines** will be summarized by visit and treatment group for continuous laboratory tests. No statistical comparisons between treatments will be conducted for these summaries. The mean value (and associated standard error) will be plotted by treatment group in the parent study or by V30M TTR mutation at randomization during the parent study over visits for the following laboratory parameters: platelets, creatinine clearance by CKD-EPI, Albumin, urine AC ratio, and urine PC ratio.

Summary for Albumin will also be presented based on the **parent study baseline** and the **OLE study baseline**.

All laboratory test results will be listed. Separate listings will be provided for local and central labs. The central lab listing will be based on the ADaM dataset and will include all central lab records. The local lab listing will be based on the SDTM dataset. A separate listing for platelets will be provided that includes assessment from both the local and central labs. A separate listing will contain only values outside of normal ranges. The number and percent of patients that stopped treatment because met a protocol-defined stopping rule for liver function, renal function, or platelet counts will be tabulated by treatment group of the parent study.

Additional investigation of hepatobiliary laboratory assessments, platelet counts and renal parameters will be performed, and are detailed in the sections below. In this investigation confirmed laboratory values will also be summarized.

A confirmed value is based on a consecutive lab value performed on a different day to, but within 7 days of, the initial value. If that value is in the same or worse category then the initial value is confirmed. If the consecutive value is in a better category then the initial value is confirmed using the consecutive value category. If there is no retest within 7 days then the initial value is presumed confirmed. If there are multiple results on the same day (no matter from the same lab vendor or different lab vendors), then the worst value will be utilized in the analysis.

